8.4. Methods and Procedure

If a technical malfunction of the ARES was to occur, a conventional bronchoscope will be used at the discretion of the investigator. The study procedure may be recorded with an external video camera for educational purposes only.

Bronchoscopy:

Sedation: General anesthesia will be administered by an anesthesiologist per standard care at El Camino Hospital in a dedicated bronchoscopy suite. Patients will be continuously monitored throughout the procedure as per standards practices at El Camino Hospital.

Airway inspection: When adequate sedation has been given, the bronchoscope (BF-P190, Olympus, Tokyo, Japan) will be inserted into the tracheobronchial tree through endotracheal tube and a standard airway inspection will be performed.

Robot-assisted bronchoscopy: Following standard airway inspection, the robotic system will be positioned in an operative position. A study investigator will connect the sterile robotic bronchoscope to the light source and camera box, manually inserted the bronchoscope into the endotracheal tube and attached it to the robot. Then, the investigator will remotely advance the bronchoscope into the bronchial tree using the endoscope controller and will navigate it into the targeted lobar segment using EM navigation. In addition to direct visualization, monoplanar fluoroscopy may be used to provide additional viewing method during all procedures.

CONFIDENTIAL

REBUS: Once the bronchoscope was positioned within 2 cm from the targeted lesion, REBUS probe will be passed to confirm localization of a targeted lesions. The REBUS images will be recorded and classified as either concentric or eccentric.

TBNA and Biopsy: An aspiration needle will be first inserted into the working channel and advanced along the same pathway to the lesion. Four needle aspirations will be performed from the targeted lesion. Secondly, four biopsies will be performed using forceps and acquired samples will be placed in formalin.

ROSE: Needle aspiration samples will be plated on slides for immediate on-site evaluation by the cytopathology team, as per the standard practice of the Interventional Pulmonology team at El Camino Hospital. Rapid on-site evaluation (ROSE) of acquired cytologic specimen will be performed in all cases.

ROSE diagnostic: If ROSE provides a definitive diagnosis, the procedure will be completed.

ROSE non-diagnostic: If ROSE does not provide a definitive diagnosis, conventional bronchoscopy will be performed.

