8.5. Post Bronchoscopy

Prior to hospital discharge, all subjects will be evaluated for adverse events. These data will be captured in the Case Report Forms. The patient will be managed post-operative in a dedicated post-procedure area as per standard practices at El Camino Hospital. The subject will be monitored for postoperative symptoms and will undergo a chest X-ray within 2 hours from the conclusion of the procedure, to rule out complications such as pneumothorax. Prior to hospital discharge, the investigator and/or designee will arrange a follow-up appointment.

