14.1. General

All adverse events (AE) and serious adverse events (SAE) will be monitored from the time of enrollment through the end of follow-up.

An AE is defined as any undesirable clinical occurrence in a patient whether or not it is considered to be device related. In addition, the definition of AE applies to any event with an onset post study procedure or to any underlying diseases, present at baseline, that exacerbate in severity post study procedure. Therefore, an underlying disease that was present at the time of enrollment is not reported as an AE, but any increase in the severity of the underlying disease is to be reported as an AE. All reported AEs must be recorded in the database. A description of the event, including the start date, resolution date, action taken, and the outcome should be provided, along with the Investigator's assessment of the relationship between the AE, the study treatment and the study procedure.

The following definitions for rating severity of adverse events will be used:

- Mild: Awareness of signs or symptoms, but easily tolerated; are of minor irritant type; causing no loss of time from normal activities; symptoms would not require medication or a medical evaluation; signs or symptoms are transient.
- Moderate: Interferes with the subject's usual activity and/or requires symptomatic treatment.
- Severe: Symptom(s) causing severe discomfort and significant impact of the subject's usual activity and requires treatment.

A serious adverse event (SAE) is defined as an event which leads to:

- Death due to any cause
- Life-threatening condition
- Results in persistent or significant disability/incapacity
- Requires in-patient hospitalization or prolonged hospitalization
- Necessitates an intervention to prevent a permanent impairment of a body function or permanent damage to a body structure
- Results in congenital abnormality

All SAE's will be reported.

Device-Related Adverse Event: an adverse event is considered to be device-related when, in the judgment of the Investigator, the clinical event has a reasonable time sequence associated with use of the AURIS ROBOTIC ENDOSCOPY SYSTEM (ARES) and is unlikely to be attributed to concurrent disease or other procedures or medications. It is reasonable to believe that the system directly caused or contributed to the adverse event.

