Procedure-Related Adverse Event: an adverse event is considered to be procedure-related when, in the judgment of the Investigator; it is reasonable to believe that the event is associated with the assigned study procedure and is not specific to the **AURIS ROBOTIC ENDOSCOPY SYSTEM (ARES)** used. Other products, surgical techniques, or medications required specifically for the procedure are likely to have contributed to the occurrence of the event.

Concomitant Medication-Related Adverse Event: an adverse event is considered to be concomitant medication related when, in the judgment of the Investigator, it is reasonable to believe that the event is associated with concomitant medications used in conjunction with the **AURIS ROBOTIC ENDOSCOPY SYSTEM (ARES)** and is not otherwise specific to the **AURIS ROBOTIC ENDOSCOPY SYSTEM (ARES)** (e.g. bleeding associated with anticoagulation medication).

Pre-Existing Condition-Related Adverse Event: an adverse event is considered to be related to a pre-existing condition when, in the judgment of the Investigator, it is reasonable to believe that the event is associated with the subject's pre-existing condition and is not specific to the AURIS ROBOTIC ENDOSCOPY SYSTEM (ARES) or procedure. Pre-existing conditions that are aggravated or become more severe during or after the procedure should be evaluated on a case-by-case basis to

determine if the event may be more appropriately classified as device-related or procedure-related.

Auris Surgical Robotics, Inc., or its designee, in cooperation with the Investigator, will assess all adverse events considered to be device-related for potential reportability to the FDA and other regulatory authorities as an Unanticipated Adverse Device Effect (UADE).

The Investigator should follow all unresolved serious adverse events until the events are resolved, the subject is lost to follow-up, the subject has withdrawn consent, or the adverse event is otherwise explained.

For purposes of this study, the following events are not likely to be device-specific adverse events, because they are typical procedure/anesthesia related adverse events normally expected to occur in conjunction with these types of bronchoscopic procedures / post-procedure, or are associated with customary, standard care of subjects undergoing these procedures:

- Any pre-planned surgical procedures
- Bleeding
- Pneumothorax
- Post-procedure respiratory insufficiency

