14.2. Reporting of Serious and Non-Serious Adverse Events

14.2.1. General Reporting Requirements (Serious & Non-Serious Adverse Events)

All serious and potentially device- and/or procedure-related adverse events must be recorded on the Adverse Event CRF by the Investigator (or designee). The report should include: severity, duration, action taken, treatment outcome and relationship of the adverse experience to the study device, procedure, concomitant medications, pre-existing condition, etc. (i.e., unrelated, related or relationship unknown).

In the case of serious adverse events, procedure and/or device observations and malfunctions, medical record documentation (e.g. procedure notes, operative notes, discharge summary, relevant progress notes, imaging or lab studies) must be provided to Auris or its designee.

The following criteria must also be adhered to by the Investigator in the case of serious adverse events:

- The Adverse Event CRF must be signed by the Investigator or Co-Investigator.
- It is the responsibility of the Investigator to inform their IRB of serious adverse events as required by their IRB procedures and in conformance with FDA and local regulatory requirements.

All serious adverse events must be reported by the Investigator (or designee) to the sponsor, within 24 hours of learning of the adverse event via CRF. The Auris contact information for questions is:

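### The device-related adverse event definition in 14.1 gives opposite answers for shared-cause events, and the UADE screen built on it is narrower than the UADE definition

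*Protocol*

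**What the plan says.** Section 14.1 of the protocol defines a device-related adverse event in two sentences. The first asks, in the investigator's judgment, for a reasonable time sequence with ARES use and that the event "is unlikely to be attributed to concurrent disease or other procedures or medications". The second reads: "It is reasonable to believe that the system directly caused or contributed to the adverse event".

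The same section defines a procedure-related event as one not specific to the ARES, and adds: "Other products, surgical techniques, or medications required specifically for the procedure are likely to have contributed to the occurrence of the event". It then gives guidance that "the following events are not likely to be device-specific adverse events"; the list includes bleeding, pneumothorax and post-procedure respiratory insufficiency. The investigator keeps the final judgment.

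For UADE purposes, 14.1 says that the sponsor or its designee, with the investigator, "will assess all adverse events considered to be device-related for potential reportability to the FDA" and other authorities. Section 14.2.1 has the relationship to device, procedure, medication and pre-existing condition recorded as "i.e., unrelated, related or relationship unknown".

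Under 8.4, each procedure starts with a manual airway inspection. Four needle aspirations and four forceps biopsies through the ARES follow. After that: "If ROSE does not provide a definitive diagnosis, conventional bronchoscopy will be performed". (The next paragraph of 8.4 makes this optional; the two should be reconciled.) Under 8.5 the subject "will undergo a chest X-ray within 2 hours from the conclusion of the procedure".

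**The concern.** A safety count depends on the rule that sorts events into it. Here the rule has two tests that disagree for the kind of event this procedure is most likely to produce: one with more than one plausible cause. If the first sentence governs, an event to which the ARES contributed is not device-related whenever a biopsy tool, a second bronchoscope or a drug is also a likely cause. If the second governs, it is. Two careful investigators could classify the same event differently, and each would be following the protocol.

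The error would mostly run one way. The procedure-related definition and the guidance list both move shared-cause events away from the device. A low device-related count could then partly reflect the definition. The UADE screen depends on the same classification, so an event sorted elsewhere would not enter it.

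**Working it through.** The protocol states no adverse event rate, alpha or power, so there is no figure to reproduce. The check is mainly a comparison of texts.

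**1. The two sentences of the device-related definition (14.1).**

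| Likely cause | Sentence one (not likely due to something else) | Sentence two (caused or contributed) |
|---|---|---|
| ARES alone | met | met |
| Biopsy tool, other scope or drug alone | not met | not met |
| ARES and one of these together | not met | met |

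The tests differ only in the third row, and 14.1 does not say which prevails.

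**2. How often the third row can arise.** Under 8.4 the ARES is used to reach the lesion and tools are then passed through its channel. Section 1.1 treats those tools as outside the device under study. A competing cause is therefore present in nearly every completed case, and a second one where conventional bronchoscopy follows.

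**3. Whether an ARES contribution is plausible for the listed events.** The porcine study in 3.2 (10 animals) had one pneumothorax, while the user was navigating without vision and testing the system's reach. Section 1.2.1 lists lung collapse and bleeding among the risks of bronchoscopy without biopsy. The 14.1 guidance list nevertheless names pneumothorax and bleeding as unlikely to be device-specific.

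**4. Where a shared-cause event ends up if classed as procedure-related only.**
- Synopsis: the primary safety endpoint covers device-related or procedure-related events, so it is counted.
- Section 9.3: the endpoint covers device-related events only, so it is not counted.
- Section 9.4: the secondary endpoint takes complications not related to the device, so it could be reported there.

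**5. UADE.** The screen in 14.1 starts from events already considered device-related. The definition in 19.2 covers serious, previously unidentified effects caused by the device or associated with it. A serious event of shared or unknown cause can meet the definition without entering the screen.

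**6. Illustration of size.** Let n = 60 (the maximum in 5.2), p = the true rate of ARES-contributed events and m = the share of them classed elsewhere. Both p and m are assumptions, with at most one such event per subject and subjects independent. The expected count is n·p·(1 − m), and the chance of seeing none is (1 − p(1 − m))^n.

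| p | m = 0 | m = 50% | m = 75% |
|---|---|---|---|
| 2% | 1.2 expected; none 29.8% | 0.6; 54.7% | 0.3; 74.0% |
| 5% | 3.0; 4.6% | 1.5; 21.9% | 0.75; 47.0% |
| 10% | 6.0; 0.2% | 3.0; 4.6% | 1.5; 21.9% |

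For p = 5% and m = 50%: (1 − 0.025)^60 = 0.219. Zero device-classed events in 60 gives an exact one-sided 95% upper limit of 1 − 0.05^(1/60) = 4.9%. That limit would not cover ARES contributions classed elsewhere.

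**The case against.** A reader might infer that ARES contributions are certain to drop out of the safety endpoint. The documents do not support that, for several reasons.

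- The synopsis keeps procedure-related events in the primary safety endpoint. The loss follows only under 9.3, and even there the event is relabelled, not removed from the data.
- The other procedures in sentence one may mean procedures outside the study, since 14.1 has its own class for events of the study procedure. On that reading the clause can often be met. The text does not say so, however, and the procedure-related definition and guidance list still pull shared-cause events away from the device.
- Attribution is by investigator judgment. Subjects are monitored continuously during the procedure (8.4) and adverse events are followed from enrollment (14.1). The X-ray is a scheduled check, not the first chance to notice an event, and an event seen before conversion cannot be put down to the second bronchoscope.
- Section 14.2.1 asks for the relationship to several possible causes, so recording more than one is not barred. Serious events reach the sponsor within 24 hours (14.2.1, 20.3), and the sponsor reviews unanticipated serious events without a device filter (18.3). A UADE must also be previously unidentified, and bleeding and lung collapse are already listed risks. They would qualify only by unexpected severity or incidence.
- Biopsy through the ARES is the plan, but malfunction (8.4), intra-procedure exclusion (6.1.3) and withdrawal before insertion (6.2) are exceptions.

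It is also tempting to assume that 20–50% of 60 subjects convert and to present the resulting 12–30 as the size of the problem. The protocol gives no conversion rate, and those would be converted subjects, not misclassified events.

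These points reduce the consequence from certain to possible. They do not settle which sentence of the definition prevails, and they do not bring the UADE screen into line with its definition.

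**Conclusion.** The point holds as a conflict within 14.1 and as a mismatch between the UADE screen there and the definition in 19.2. The result is a risk that events to which the ARES contributed are classed as not device-related, in a direction that favours the device. Loss from the primary safety endpoint depends on 9.3 prevailing over the synopsis.

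The size cannot be fixed from the protocol, because neither the event rate nor the share reclassified is given. Over the assumed ranges in the working, reclassifying half of the events lifts the chance of a zero count from 29.8% to 54.7% at a 2% true rate, and from 0.2% to 4.6% at 10%. The only clinical bronchoscopy experience reported (15 patients, three non-serious adverse events judged unrelated; 1.1) does not narrow this. The wording should be corrected; the point does not invalidate the study.

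**What to change.** 1. In 14.1, delete the exclusive clause and use one test: an event is device-related if the ARES caused it or contributed to it, even if biopsy tools, another bronchoscope or medication also contributed.
2. State that one event may be both device-related and procedure-related. Align the procedure-related definition and the guidance list with this, so that bleeding or pneumothorax is device-related when the ARES contributed.
3. Screen for UADE all serious events possibly associated with the device, including those of unknown relationship.
4. On the adverse event CRF, note whether the event was first observed before or after any conversion to conventional bronchoscopy.
5. Report events of unknown relationship separately, without counting them automatically as device-related.
6. Reconcile the primary safety endpoint in the synopsis with 9.3, because the consequence of any classification depends on it.

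A fluoroscopic check for pneumothorax before conversion should not be added on this account. It would be a new assessment: the protocol uses fluoroscopy only as a viewing aid.

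The cost is a protocol amendment and one CRF item, with no new procedure. The downside is that the reported device-related event rate may be somewhat less favourable.

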14.2. Reporting of Serious and Non-Serious Adverse Events

14.2.1. General Reporting Requirements (Serious & Non-Serious Adverse Events)

All serious and potentially device- and/or procedure-related adverse events must be recorded on the Adverse Event CRF by the Investigator (or designee). The report should include: severity, duration, action taken, treatment outcome and relationship of the adverse experience to the study device, procedure, concomitant medications, pre-existing condition, etc. (i.e., unrelated, related or relationship unknown).

In the case of serious adverse events, procedure and/or device observations and malfunctions, medical record documentation (e.g. procedure notes, operative notes, discharge summary, relevant progress notes, imaging or lab studies) must be provided to Auris or its designee.

The following criteria must also be adhered to by the Investigator in the case of serious adverse events:

- The Adverse Event CRF must be signed by the Investigator or Co-Investigator.
- It is the responsibility of the Investigator to inform their IRB of serious adverse events as required by their IRB procedures and in conformance with FDA and local regulatory requirements.

All serious adverse events must be reported by the Investigator (or designee) to the sponsor, within 24 hours of learning of the adverse event via CRF. The Auris contact information for questions is:

14.3. Device Failures and Malfunctions

All reported device observations, malfunctions or failures of the Auris ARES are required to be documented in the CRF. Device failures and malfunctions should also be documented in the patient's medical record.

NOTE: Device failures or malfunctions are NOT to be reported as adverse events. However, if there is an adverse event that results from a device failure or malfunction, that specific event would be recorded in the usual way.

15.Ethical Considerations

15.1. Study Conduct & the Declaration of Helsinki

The Study will be performed in accordance with the relevant parts of Title 21 CFR Parts 812, 50, 54, 56 and ISO 14155-1 / 14155-2.1; the ICH Guidelines for Good Clinical Practices (E6), the Declaration of Helsinki, and any regional and/or national regulations.

15.2. Institutional Review Board/Ethics Committee

A copy of the protocol, proposed Informed Consent form, other written patient information and any proposed advertising material must be submitted to the IRB for written approval. A copy of the written IRB approval of the protocol and Informed Consent form must be received by Auris Surgical Robotics, Inc. before recruitment of patients into the study and shipment of product.

The Investigator must submit and, where necessary, obtain approval from the IRB as well as the FDA, for all subsequent significant protocol amendments and significant changes to the Informed Consent form. The Investigator should notify the IRB of deviations from the protocol or SAEs and UADEs occurring at the site and other SAE/UADE reports received from Auris Surgical Robotics, Inc in accordance with local procedures.

The Investigator will be responsible for obtaining annual IRB approval and renewal throughout the duration of the study. Copies of the Investigator's reports and the IRB continuance of approval must be sent to Auris Surgical Robotics, Inc.

15.3. Informed Consent Form

A sample Informed Consent form is provided in Section 21 Attachment 2 for the Investigator to prepare for use at his/her site. The written Informed Consent documents should be prepared in the language(s) of the potential patient population.

The reviewing IRB and the sponsor must first approve the Informed Consent forms that are used. The Informed Consent forms that are used should be in accordance with the current guidelines as outlined by the Good Clinical Practices (GCP) guidelines, Declaration of Helsinki and the International Conference on Harmonization (ICH).

Prior to participation in the clinical Study, each patient must give written Informed Consent after the context of the study has been fully explained to the patient in language that is easily understood by the patient. The patients must also be given the opportunity to ask questions and have those questions answered to their satisfaction.

Written Informed Consent must be recorded appropriately by means of the patient's, or their legal representative's dated signature. The patient will receive a copy of the Informed Consent form.

15.4. Amending the Protocol

An Investigator may not make protocol changes without prior approval by Auris Surgical Robotics. All significant protocol changes that may affect the following must be submitted and approved by the IRB before initiating the change:

- validity of the data or information resulting from the completion of the approved protocol;
- relationship of the likely subject risk to benefit relied upon to approve the protocol;
- scientific soundness of the investigational plan, or;
- rights, safety, or welfare of the human subjects involved in the investigation.

Auris will submit a copy of the protocol amendment to the Investigator for his IRB to review. The investigative site must send Auris Surgical Robotics a copy of the IRB approval letter for the protocol amendment.

Auris may make certain administrative changes to the protocol without prior approval of the IRB. The site IRB will be notified of these changes.

